5.1.2 Patient Enrolment

An overview of enrolled patients since previous report and total patients enrolled will be reported for each country (**Table 3**).

5.1.3 Patient Demographics

The following demographics characteristics will be summarised for enrolled patients in the analysis set (**Table 4.1**):

- Gender (male, female)
- Age (years) at Informed Consent date
- Race or ethnicity as recorded in the medical record, if available (White, Black, Hispanic, Asian, other). Note: Patients may have more than one race recorded.
- Body weight (Note: Patient weights were either obtained from medical record or were prospectively collected after administration of vernakalant IV in a supplemental data collection tool for prospectively enrolled patients.)
- Method of measurement for weights (direct measurement, patient-reported, estimated from health professional, unknown, recorded after vernakalant IV administration)
- Reason patient weight not measured prior to vernakalant IV administration (patient bed-bound, weighing equipment unavailable or broken, unknown, other)
- Body mass index (BMI)

Gender and age will also be summarised for screened patients and for screened but not enrolled patients (**Table 4.2**):

5.2 Hospital Characteristics and Medical Encounter

The following hospital characteristics and medical encounter will be summarised at the patient level (**Table 1.1**):

- Hospital type (Public hospital, private hospital, university hospital, regional/community hospital, other) from Site Qualification Questionnaire (SQQ).

- Hospital size (large, small). Hospital size based on number of beds. Large hospitals defined as 300 or more beds; small hospitals defined as fewer than 300 beds. Number of beds based on direct hospital and site contact.
- Hospital admission (emergency, planned admission, transfer from another facility).
- Department in which vernakalant IV was administered (Intensive Care Unit (ICU), Coronary Care Unit (CCU), Post-Surgical ICU, Emergency Department, Operating Room/Surgical, Cardiac Procedure Room, General Medical Ward, Other).
- Total hospital length of stay (hours) and length of stay by department in which vernakalant IV was administered. Note: total hospital length of stay may be converted to days.

5.3 Receipt and Use of Risk Minimisation Tools

Data regarding use and receipt of Pre-Infusion Checklist and HCP Educational Card (resulting from Pharmacovigilance Risk Assessment Committee [PRAC] feedback) were collected starting on August 9, 2014. **Table 1.2** includes information on whether the Pre-Infusion Checklist was used prior to vernakalant IV administration, and **Table 1.3** includes information on whether the site investigator and/or co-investigator received and read the HCP Educational Card.

5.4 Primary Objective # 1: Incidence of HOIs

Based on the primary objective #1, the incidence of HOIs reported from the start of first infusion through the first 24 hours following the last infusion of vernakalant IV or until discharge/end of medical encounter (whichever occurs earlier) will be calculated as the number of patients who have at least one specific pre-specified event starting from the beginning of the study period, divided by total number of patients enrolled and treated with vernakalant, multiplied by 100. The incidence of HOIs as designated by the investigator is summarised by method of enrolment (overall, prospective and retrospective) in **Table 8.1.1** to **Table 8.1.3** and the incidence of HOIs as designated by the SRC by method of enrolment (overall, prospective and retrospective) are displayed in **Table 8.2.1** to **Table 8.2.3**. The incidence of HOIs as designated by either the investigator or the SRC by method of enrolment (overall, prospective and retrospective) is displayed in **Table 8.3.1** to **Table 8.3.3**. Patients with more than one HOI will be counted once in the numerator. Patients with more than one HOI event (either more than one HOI within the same HOI type, or multiple HOI types) will be identified in the report, along with a footnote in the Table 8 series.

Results from the SRC review, including the SRC's classification of the event and whether the event qualifies as a study-defined HOI, are included in some of the HOI and SAE tables and listings (**Listings 1a, 2a, 7, and 8**). A listing of all SAEs and HOIs, both defined by the investigator and by the SRC, is shown in **Listing A**.

Definitions for HOIs (significant hypotension, significant ventricular arrhythmia, significant atrial flutter, and significant bradycardia) are provided in Section 3.1. For the HOI significant bradycardia, the incidence of bradycardia requiring electrical pacing (temporary or permanent) and the incidence of patients experiencing any other SAEs involving bradycardia (but not

requiring temporary or permanent pacing) will be reported both separately and combined. A study definition of SAEs involving bradycardia is conservatively added to the investigator assessment based on a list of MedDRA terms that would be considered to be SAEs involving bradycardia (**Appendix 2**). Therefore “investigator assessment” includes bradycardia HOIs designated as such per the investigator and/or study definition. MedDRA code version 14.0 used to identify SAEs are consistent with clinical development program.

For patients who receive one infusion during a treatment episode, the follow-up period for HOIs is from the start of this infusion through the first 24 hours, or until discharge/end of medical encounter, whichever occurs earlier.

For patients who receive more than one infusion during a treatment episode, the follow-up period for HOIs is from the start of the first infusion through the first 24 hours following the start of the last infusion, or until discharge/end of medical encounter, whichever occurs earlier.

Because HOIs are expected to be rare events, Clopper Pearson (Exact) confidence intervals will be constructed around the point estimate of the incidence for each HOI. [3] Numbers and rates of HOIs will also be presented according to time intervals since start of first vernakalant infusion, i.e., 0 to less than 2 hours, 2 to less than 4 hours, and 4 hours to a maximum of 24 hours.

The primary analysis for HOI incidence is the 0-2 hour post infusion time point. Given the lower expected sample size, vernakalant's mode of action and the non-interventional nature of the study design, the 2-4 hour and 4-24 hour post infusion time points are considered secondary and tertiary analyses, respectively.

The HOI incidence for each time interval will be calculated as follows.

For each time interval, the numerator will be the number of patients with at least one HOI with an onset date and time in the time interval occurring among patients enrolled and treated with vernakalant. The denominator will be the number of patients enrolled and treated with vernakalant.

For the 0-<2 hour time interval, the number of patients with at least one HOI with an onset date and time in the 0-2 hour interval (interval is from start date and time of vernakalant administration to 1:59:59 following start date and time of vernakalant administration) divided by the number of patients enrolled and treated with vernakalant.

For the 2-<4 hour time interval, the number of patients with at least HOI with an onset date and time in the 2-<4 hour interval (interval is from 2:00:00 following start date and time of vernakalant administration to 3:59:59 following start date and time of vernakalant administration) divided by the number of patients enrolled and treated with vernakalant.

For 4-24 hour time interval, the number of patients with at least one HOI with an onset date and time in the 4-24 hour interval (interval is from 4:00:00 following start date and time of vernakalant administration to 24:00:00 following start date and time of vernakalant administration) divided by the number of patients enrolled and treated with vernakalant

Characteristics of patients with HOIs, which may include prior medical history, presenting conditions, medication use, dosing/administration of vernakalant IV, concomitant therapies, and assessment of relatedness as provided by the investigator will be summarised as a narrative in the listing of individual HOI events in study reports. Case narratives will be provided in **Listing 1b** and **Listing 2b** for each HOI and SAE regardless of the relationship to vernakalant and will describe patients with more than one HOI event reported. Listings will be by-event (i.e., patient with multiple events will be repeated for each event type) and will contain the patient's case narrative for each event type.

5.5 Primary Objective #2: Administration of Vernakalant Consistent with Weight-Based Dosing and Patient Monitoring

Based on Primary Objective #2, distributions of patient body weight, number of infusions, total dose administered with each IV infusion and administration duration stratified by body weight (<113 kg and \geq 113 kg) will be summarised (**Table 9**). Body weight and details of dosing and administration (indication, number of infusions, dose in mg and mg/kg, percentage of weight-based dosing recommendations, duration, whether stopped prematurely, and the reasons for stopping) will be presented separately for each body weight group.

Percentage of weight-based dosing recommendation per label will be calculated as actual vernakalant IV dose divided by the recommended vernakalant IV dose, multiplied by 100. The measure will range from greater than 0% to above 100%, with 100% indicating that dose is equal to recommended dose, calculated per first or second infusion. The recommended vernakalant administration dose is weight-based. If patient's body weight is < 113 kg, total dose for initial and second infusions should be 3 mg/kg and 2 mg/kg, respectively, over a 10 minute period. If the patient is \geq 113 kg, total dose for initial and second infusions should be 339 mg and 226 mg, respectively, over a 10 minute period. For example, a patient weighing less than 113 kg receiving one infusion of vernakalant at a dose of 2.5 mg/kg would have a percentage of weight-based dosing recommendation per label of 83.3% (recommended dose is 3 mg/kg). A patients weighing greater than 113 kg who received an initial infusion of vernakalant at a dose of 350 mg would have a value of 103.2% (recommended dose is not to exceed 339 mg).

For exploratory analysis, listings of patients with vernakalant IV stopped prematurely, those whose first infusion was shorter than 9 minutes and those whose second infusion was shorter than 9 minutes, (**Listing 5a**, **5b**, and **5c**, respectively) will be produced. The listing will include the following data elements: patient ID, age, gender, weight, country, number of infusions, dose (in mg and mg/kg), percentage of weight-based dose recommendation, duration (minutes). Dose, percentage of weight-based dosing recommendation, and duration will be reported for the first infusion and second infusion, if applicable.

For **Listing 5a**, the reason for premature stopping of vernakalant (e.g., successful cardioversion, non-serious adverse event, other verbatim responses) will also be included. Patients with early termination of vernakalant IV will be included in **Table 9** as a separate subgroup if the total number of patients with vernakalant stopped prematurely reaches a minimum of 10% of patients, otherwise patients with reported early termination of the infusion will be included in the overall analysis population presented in **Table 9** with appropriate description in report text and table footnotes.

Additionally, data on patient's body weight in kg (x-axis) and total dose in mg (y-axis) for first infusion and second infusion, if applicable, will be presented graphically. Given the large number of overlapping data points, a jittered scatterplot may be used (**Figure 2**).

Monitoring of patients during and after vernakalant IV administration by number of infusions include (**Table 14a, 14b**):

- Frequency and duration of blood pressure monitoring
- Blood pressure monitoring by healthcare provider (nurse, physician, other)
- Continuous monitoring of cardiac rhythm (yes, no)
- Cardiac rhythm monitoring by healthcare provider (nurse, physician, other)

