3.4 Derived Variable Definitions

The following derived/calculated values will be used:

- Age at enrolment = [(date of informed consent – date of birth) + 1]/365.25, or self-reported age if date of birth is not available.
- BMI = Weight (Kg)/Height (m)². English standard units should be converted to international or metric units.
- (S)AE or HOI onset in days and time (in hours or minutes) following vernakalant IV infusion = date/time of onset or (S)AE-date – date/time of start of first infusion.
- Duration or period = (stop time – start time). Note there are key durations that include, but are not limited to, duration of vernakalant IV infusions and duration of HOI and SAE.
- Vernakalant IV dose per body weight = vernakalant IV dose (mg) / body weight (kg).
- Duration of time to conversion to sinus rhythm = (date/time of conversion to sinus rhythm – date/time of start of first infusion).
- Percentage of weight-based dosing recommendation per label (%) = (Vernakalant IV dose [mg/kg] / Recommended vernakalant IV dose [mg/kg]) * 100. Range from 0% to above 100%, with 100% indicating that dose is equal to recommended dose, calculated per first or second infusion. Patients with cumulative doses greater than the maximum recommended dose will be noted (overall and for first and second infusion, separately).
- Duration of current AF in hours = (Vernakalant administration date/time - AF onset date/time).

- Time since first AF diagnosis = (Start date of Vernakalant IV administration - Date of first AF diagnosis).
- Rate of conversion to sinus rhythm for at least one minute within 90 minutes of start of first vernakalant IV administration = (Number of relevant patients converted to sinus rhythm for at least one minute within 90 minutes of start of first vernakalant IV administration) / (Total number of relevant patients administered vernakalant IV). Rate of conversion can be evaluated based on different types of patients, e.g. all patients receiving vernakalant IV or all such patients with other restrictions.
- Elevated liver enzymes (inclusive of possible abnormal liver function or liver injury) = an increase above upper limit of normal (ULN) for alanine aminotransferase (ALT), aspartate aminotransferase (AST), or total bilirubin (TB) or conjugated bilirubin. [1,2]
- Total hospital length of stay (hours) = (Date/time of discharge or release of facility – Date/time of hospital admission).

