4.4 Handling Withdrawals and Missing Data

There will be no imputation of missing data. Data will be presented and summarised as it was recorded. Reasonable attempts should be made by the treating physician and/or site personnel to limit the amount of missing data. The proportion of missing data is expected to be low for this study, especially with regard to the details of administration of vernakalant IV and concomitant therapies, collected laboratory values, and occurrence of HOIs during the brief, in-hospital follow-up period. Reasonable attempts will be made to limit the amount of missing medical history and presenting condition data to ensure that important information is captured.

Prospective supplemental data collection of study-specific data elements, such as patient's weight, heart failure NYHA functional class, vernakalant administration and patient monitoring is expected to limit missing data.

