⁴As recorded on the Pharmacologic Cardioversion or Concomitant Medication CRF. Class I or class III anti-arrhythmics use with missing drug start date/time, vernakalant administration date/time, or route classified as unknown.

Table 12a.1 Frequency of Pharmacological Cardioversion Using Intravenous Anti-Arrhythmics to Restore Sinus Rhythm by Timing in Relation to Vernakalant IV Administration (Analysis Set)

| Characteristic | Within 4 hours prior to the start of first vernakalant infusion ^{1,2} | Within 4 hours subsequent to the start of first vernakalant infusion ^{1,2} | Within 90 minutes subsequent to the start of first vernakalant infusion ^{1,2} | Any time during the hospitalisation/medical encounter (but not within 4 hours prior or subsequent to the start of first vernakalant infusion) ^{1,2} | Overall |
|---|---|--|---|--|---------|
| Administration of Other Intravenous Anti-Arrhythmic Agents for Pharmacologic Cardioversion (per patient) | | | | | |
| n | xx | xx | xx | xx | |
| Yes | xx (xx.x%) | xx (xx.x%) | xx (xx.x%) | xx (xx.x%) | xx (%) |
| No | xx (xx.x%) | xx (xx.x%) | xx (xx.x%) | xx (xx.x%) | xx (%) |
| Missing | xx | xx | xx | xx | |
| Number of IV AA Administrations (episodes) | xx | xx | xx | xx | |
| Type of Rhythm Disorder, if Yes³ | | | | | |
| n | xx | xx | xx | xx | |
| Atrial fibrillation | xx (xx.x%) | xx (xx.x%) | xx (xx.x%) | xx (xx.x%) | xx (%) |
| Atrial flutter | xx (xx.x%) | xx (xx.x%) | xx (xx.x%) | xx (xx.x%) | xx (%) |
| Ventricular tachycardia | xx (xx.x%) | xx (xx.x%) | xx (xx.x%) | xx (xx.x%) | xx (%) |
| Ventricular fibrillation | xx (xx.x%) | xx (xx.x%) | xx (xx.x%) | xx (xx.x%) | xx (%) |
| Other | xx (xx.x%) | xx (xx.x%) | xx (xx.x%) | xx (xx.x%) | xx (%) |
| Missing | xx | xx | xx | xx | |
| Class of Anti-arrhythmic^{3,4} | | | | | |
| n | xx | xx | xx | xx | |
| IA | xx (xx.x%) | xx (xx.x%) | xx (xx.x%) | xx (xx.x%) | xx (%) |
| IB | xx (xx.x%) | xx (xx.x%) | xx (xx.x%) | xx (xx.x%) | xx (%) |
| IC | xx (xx.x%) | xx (xx.x%) | xx (xx.x%) | xx (xx.x%) | xx (%) |
| II | xx (xx.x%) | xx (xx.x%) | xx (xx.x%) | xx (xx.x%) | xx (%) |
| III | xx (xx.x%) | xx (xx.x%) | xx (xx.x%) | xx (xx.x%) | xx (%) |
| IV | xx (xx.x%) | xx (xx.x%) | xx (xx.x%) | xx (xx.x%) | xx (%) |
| Other AA/Class V | xx (xx.x%) | xx (xx.x%) | xx (xx.x%) | xx (xx.x%) | xx (%) |
| Missing | xx | xx | xx | xx | |
| Intravenous Anti-arrhythmics³ (Class I & III) | | | | | |
| n | xx | xx | xx | xx | |
| Class I | | | | | |

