| Flecainide | xx (xx.x%) | xx (xx.x%) | xx (xx.x%) | xx (xx.x%) | xx (%) |
| <Other class I medications, if used> | | | | | |

| Characteristic | Within 4 hours prior to the start of first vernakalant infusion ^{1,2} | Within 4 hours subsequent to the start of first vernakalant infusion ^{1,2} | Within 90 minutes subsequent to the start of first vernakalant infusion ^{1,2} | Any time during the hospitalisation/medical encounter (but not within 4 hours prior or subsequent to the start of first vernakalant infusion) ^{1,2} | Overall |
|--|---|--|---|---|---------|
| Class III | | | | | |
| Amiodarone | xx (xx.x%) | xx (xx.x%) | xx (xx.x%) | xx (xx.x%) | xx (%) |
| Ibutilide | xx (xx.x%) | xx (xx.x%) | xx (xx.x%) | xx (xx.x%) | xx (%) |
| Sotalol | xx (xx.x%) | xx (xx.x%) | xx (xx.x%) | xx (xx.x%) | xx (%) |
| < Other class III medications, if used > | xx (xx.x%) | xx (xx.x%) | xx (xx.x%) | xx (xx.x%) | xx (%) |
| Missing | xx | xx | xx | xx | |

Note: Total n for each variable includes non-missing observations. Percentages, where applicable, are calculated with non-missing observations in denominator unless otherwise noted.

¹ Includes patients administered IV anti-arrythmic agents for pharmacological cardioversion during the specified time during the hospitalisation/medical encounter. First column includes administration within 4 hours prior to the start of first vernakalant infusion. Second column includes administration within 4 hours subsequent to the start of first vernakalant infusion. Third column includes administration NOT within 4 hours prior and/or subsequent to the start of first vernakalant infusion.

² Retrospective patients may have missing vernakalant administration date/time.

³ Percentages based on number of IV AA administrations

⁴ Based on the ATC classification, except for sotalol. For the purposes of this study, study programmers manually reclassified sotalol from ATC code C07AA (Beta Blocking Agents, Non-Selective) to ATC Code C01BD (Antiarrhythmics, Class III) in the analysis datasets as consistent with the Vaughan Williams Classification of Antiarrhythmic Drugs detailed in the SAP.

Template of Table 12a.1 will be applied to the following two tables. Please note: for Table 12a.2, footnote 2 does NOT apply , and all subsequent footnote numbers should be adjusted correspondingly.

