| | Time Since First Vernakalant Infusion | | | | | | | |
|-------------|--|-------------|---|-------------|--|----------|---|-------------|
| | 0 - < 2 hours from start of first infusion (N=xxx) ¹ | | 2- < 4 hours from start of first infusion (N=xxx) ¹ | | 4- 24 hours from start of first infusion (N=xxx) ¹ | | Overall (N=xxx) | |
| | Patients n (Cumulative Incidence ¹) | Events n | Patients n (Cumulative Incidence ¹) | Events n | Patients n (Cumulative Incidence ¹) | Events n | Patients n (Cumulative Incidence ¹) | Events n |
| Any NSAE | xx (x.x%) | xx | xx (x.x%) | xx | xx (x.x%) | xx | xx (x.x%) | xx |
| SOC 1 | xx (x.x%) | xx | xx (x.x%) | xx | xx (x.x%) | xx | xx (x.x%) | xx |
| HLT 1 | xx (x.x%) | xx | xx (x.x%) | xx | xx (x.x%) | xx | xx (x.x%) | xx |
| PT 1 | xx (x.x%) | xx | xx (x.x%) | xx | xx (x.x%) | xx | xx (x.x%) | xx |
| PT 2 | xx (x.x%) | xx | xx (x.x%) | xx | xx (x.x%) | xx | xx (x.x%) | xx |
| SOC 2 | xx (x.x%) | xx | xx (x.x%) | xx | xx (x.x%) | xx | xx (x.x%) | xx |
| HLT 2 | xx (x.x%) | xx | xx (x.x%) | xx | xx (x.x%) | xx | xx (x.x%) | xx |
| PT 1 | xx (x.x%) | xx | xx (x.x%) | xx | xx (x.x%) | xx | xx (x.x%) | xx |
| PT 2 | xx (x.x%) | xx | xx (x.x%) | xx | xx (x.x%) | xx | xx (x.x%) | xx |

¹Cumulative incidence calculated as the number of patients who have a specific pre-specified event starting during the study period, divide by the total number of patients enrolled, multiplied by 100.

Template of Table 17.1 will be applied to the following two tables. Please make sure in the header “Analysis Set” is changed to “Prospective Patients” and “Retrospective Patients”, respectively.

[figure not shown]
Table 17.2 Non-Serious Adverse Events by System Organ Class (SOC) and Preferred Term (PT) (Final Report) – Prospective Patients

Table 17.3 Non-Serious Adverse Events by System Organ Class (SOC) and Preferred Term (PT) (Final Report) – Retrospective Patients

Table 18 Number of Patients with Missing Information for Selected Critical Fields

| Critical Field | Prospective Patients (N=xxx) | Retrospective Patients (N=xxx) | Analysis Set (N=xxx) |
|---|------------------------------|--------------------------------|----------------------|
| Height | xx (xx.x%) | xx (xx.x%) | xx (xx.x%) |
| NYHA Heart Failure Class | xx (xx.x%) | xx (xx.x%) | xx (xx.x%) |
| Smoking Status | xx (xx.x%) | xx (xx.x%) | xx (xx.x%) |
| Stop Time (for each infusion) | xx (xx.x%) | xx (xx.x%) | xx (xx.x%) |

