|-------------|-------------------|---------------------|----------------------------|-----------------------|--------------------------------------|-----------------------|------------------------------------|--------------------------|---|
| | | | | | | | | | |
| | | | | | | | | | |

¹Study Defined HOIs are included in Table 8.1 series and the Listing 1 series

²SRC-defined HOIs are included in Table 8.2 series

Listing 1a Health Outcomes of Interest (HOI) – Investigator Assessment

| Site | Patient ID | Patient Type | Age (yrs) | Gender | Country | Percentage of Weight-Based Dosing Recommendation > 110% | | HOI (MedDRA PT Term) | SRC HOI Designation | SRC Adjudication Term | Onset date/time | Timing in relation to start of first infusion (Min) |
|------|------------|--------------|-----------|--------------|---------|---|-----------------|----------------------|---------------------|-----------------------|-----------------|---|
| | | | | | | First Infusion | Second Infusion | | | | | |
| | | | | Male, Female | | Yes, No | Yes, No | | | | | |
| | | | | | | | | | | | | |

| Site | Patient ID | Patient Type | Age (yrs) | Gender | Country | Stop date/time | Duration of HOI (hours) | Initial vernakalant IV infusion (Dose 1 in mg/kg) | Second vernakalant IV infusion (Dose 2 in mg/kg) | Contraindications |
|------|------------|--------------|-----------|--------------|---------|----------------|-------------------------|---|--|-------------------|
| | | | | Male, Female | | | | | | |
| | | | | | | | | | | |

Note: Prior medical history and concomitant therapies deemed to be relevant to the presentation of each HOI will be included in the narrative summaries in Listing 1b.

Listing 1b Health Outcomes of Interest (HOI) Narratives – Investigator Assessment

| Site | Patient ID | Patient Type | Site Reported HOI | Investigator Narrative ¹ | Medical Monitor Narrative ² |
|------|------------|--------------|-------------------|-------------------------------------|--|
| | | | Yes/No | | |
| | | | | | |

¹ Narrative provided by site as reported in the SAE CRF.

²Clinical narrative provided by Medical Monitor.

Listing 2a Serious Adverse Events (SAEs) – Investigator Assessment

| Site | Patient ID | Patient Type | Age (yrs) | Gender | Country | Percentage of Weight-Based Dosing Recommendation > 110% | | MedDRA Term | | | SRC HOI Designation | SRC Adjudication Term |

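### SAP 5.4 and Tables 8.1–8.3: an HOI that cannot be timed against the start of infusion drops out of the primary 0–<2 h rate, and the tables have no category for it

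*SAP*

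**What the plan says.** SAP 5.4 and protocol 10.2 both name 0–2 hours as the primary analysis of HOI incidence. For every interval SAP 5.4 states that "the numerator will be the number of patients with at least one HOI with an onset date and time in the time interval", counted from the start of vernakalant administration, and that "The denominator will be the number of patients enrolled and treated with vernakalant". SAP 3.4 derives the timing as "date/time of onset or (S)AE-date – date/time of start of first infusion". SAP 4.4 adds: "There will be no imputation of missing data".

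Five table shells (7.1, 12a.1, 12b.1, 13a.1 and 13b.1) carry the footnote "Retrospective patients may have missing vernakalant administration date/time". Table 11 provides for the same gap: "Class I or class III anti-arrhythmics use with missing drug start date/time, vernakalant administration date/time, or route classified as unknown". Footnotes to Tables 13a.1 and 13b.1 say that their Overall column includes missing timing. The Table 8 shells have the columns 0–<2 h, 2–<4 h, 4–24 h and Overall. None of their footnotes deals with a missing onset or infusion time.

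In the protocol, 7.1.1 lists the start time of each infusion as a collected item. Section 7.2.1 lets only stop time and time to conversion be missing among the dosing items, and 7.2 makes the key variables a condition for retrospective inclusion.

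**The concern.** An HOI enters an interval only if two clock times are known: its own onset and the start of the first infusion. If either is missing, the HOI enters no interval numerator, while its patient stays in every interval denominator. No rule puts it back, and the Table 8 series does not show that it was left out.

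This touches the interval that the plan calls primary, in a study where a handful of events per HOI is expected. The gap that the SAP concedes lies in the retrospective patients, who also have their own tables (8.1.3, 8.2.3 and 8.3.3). There a single event can be the whole numerator for an HOI.

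**Working it through.** **Inputs**
- Target size 2,000, per administration (SAP 4.1).
- Incidence 0% to 0.22% per HOI over 24 h in the pooled trials (SAP 4.1). This is a 24-hour rate; no 0–2 h rate is given for these HOI definitions.
- Planned retrospective patients: 435 (protocol Appendix I, total row).
- Two-sided 95% Clopper-Pearson limits (SAP 5 and 5.4).

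**Reproducing the plan's figure.** For x events in N, lower = Beta quantile(0.025; x, N−x+1) and upper = Beta quantile(0.975; x+1, N−x), with x = pN. For p = 0.003 and N = 1,500, this gives 0.00090 to 0.00729 and a margin of 0.00729 − 0.003 = 0.0043. These round to the stated 0.001, 0.007 and 0.004. All 44 cells of SAP Table A match at three decimals.

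**Direction.** Suppose an HOI truly began in 0–<2 h but cannot be timed. The numerator falls by 1 and N is unchanged, so the rate falls by 1/N: 1/2,000 = 0.05 percentage points overall, and 1/435 = 0.23 points in the retrospective table. If the HOI truly began later, the 0–<2 h rate is unaffected. The primary rate is therefore either right or too low.

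**Expected events per HOI at the top planning rate.** 2,000 × 0.0022 = 4.4, and 435 × 0.0022 = 0.96.

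**Effect of untimed events (illustration, not an expected loss)**

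| Set | All HOIs timed | Untimed | As SAP 5.4 would report 0–<2 h |
|---|---|---|---|
| Full | 5/2,000 = 0.25% (0.08–0.58) | 1 | 4/2,000 = 0.20% (0.05–0.51) |
| Full | 5/2,000 = 0.25% (0.08–0.58) | 2 | 3/2,000 = 0.15% (0.03–0.44) |
| Retrospective | 1/435 = 0.23% (0.01–1.27) | 1 | 0/435 = 0% (0–0.84) |

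**How likely, under assumptions.** Assume that 1%, 5% or 10% of the 435 (4, 22 or 44 patients) lack an infusion time, independently of having an HOI. The chance of at least one untimed HOI is 1 − (1 − p)^k for k such patients. With an assumed risk p of 0.2% it is 0.8%, 4.3% or 8.4%. With p = 0.8% (four HOI types at 0.2% each) it is 3.2%, 16.2% or 29.8%. Neither the shares nor these risks are in the documents.

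**Can the reader recover the loss?** Only in part. Subtracting the three interval event counts from the Overall count leaves the untimed events together with any late events described next.

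**Late events (minor).** SAP 5.4 first runs follow-up to 24 h after the last infusion, and later to 24 h after the start of the last infusion. The last interval closes 24:00:00 after the start of administration, and Table 8 counts from the start of the first infusion. Take 10-minute infusions (SAP 5.5) and an assumed gap of 15–60 minutes between them. The uncovered tail is 10 + 15 = 25 to 10 + 60 = 70 minutes if the clock runs from the start of the last infusion, and 35 to 80 minutes if it runs from its end. Assume, as an extreme, that all 2,000 had two infusions and that 4.4 events were spread evenly over 1,440 minutes. The tail then holds 4.4 × 25/1,440 = 0.08 to 4.4 × 80/1,440 = 0.24 events per HOI.

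**The case against.** **The objective is still answered.** Primary Objective 1 covers treatment and the 24 hours after it. That is the Overall column, where the footnote asks only that the event began in the study period. This stands: a reader might infer that an untimed HOI is lost from the study, and it is not. The loss is confined to the interval split, but both documents name the first interval as the primary analysis.

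**HOIs are well documented.** Each is entered on the serious-event form, verified against source, adjudicated by the Safety Review Committee and given a narrative. Listing 1a prints its onset and its minutes from infusion. The missing-time footnote sits under tables covering concomitant medication and other rhythm treatment, not under Table 8, and that gap may not carry over to a few verified events. This is a good reason to expect a small effect. It does not supply a rule for the case that does occur.

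**Table 18 follows the protocol.** It counts missing stop times but not missing start or onset times. A reader might take that as an oversight, but its fields mirror the 7.2.1 list of items that may be missing, and start time is not on that list. The real discrepancy is that the SAP footnotes expect a gap which the protocol's entry condition should prevent.

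**Three further readings go too far.**
- Protocol 7.2 says that event rates would not be biased downward, and a reader might see a contradiction. That sentence concerns whether HOIs are recorded in the hospital chart, not their placement in an interval.
- The term (S)AE-date in SAP 3.4 might suggest that HOI onset is collected as a date only. It may serve only the version in days, and SAP 5.4 speaks of date and time throughout.
- Keeping full N in the later intervals might look like a wrong denominator. It is an openly stated and valid proportion of all treated patients. It simply is not the risk among those still observed.

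**Conclusion.** The point holds in a limited form. By the stated rules, an HOI without a usable onset or infusion time is absent from the primary 0–<2 h rate while its patient stays in the denominator. The resulting error is nil or downward. The Table 8 series has no category that would show it, although the SAP handles the same gap elsewhere.

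The size is probably small: 0.05 percentage points per event in 2,000, with heavily overlapping intervals, and 0.23 points in 435. It would be most visible in the retrospective tables, where about one event per HOI is expected even at the top planning rate. The documents do not support saying that such events will occur, or how often. The illustrations assume that the untimed HOI truly began within two hours, and that 435 retrospective patients are enrolled as planned.

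The change is still worth making, because it protects the declared primary safety estimate at almost no cost. The late-event mismatch is minor: it bears only on the tertiary interval, at about 0.1–0.2 events per HOI under extreme assumptions.

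**What to change.** 1. Add a time-unknown column or category, with patients and events, to Tables 8.1–8.3 for the analysis set and for each enrolment method. State in SAP 5.4 that an HOI with a missing onset time or missing infusion start goes there.
2. Add a sensitivity analysis that counts those HOIs in 0–<2 h. Label it an upper bound, since some may have begun later.
3. Report the numbers of missing infusion start times and missing HOI onset times; two lines in Table 18 would do.
4. Reconcile the footnote on missing administration times with protocol 7.2 and 7.2.1, which do not exempt start time.
5. Minor: reconcile the two statements in SAP 5.4 on whether the 24 hours run from the last infusion or from its start, and extend the last interval to the end of follow-up.
6. Optional: show the number still under observation at 2 h and 4 h beside the full-N rates, using the discharge time already collected. Keep the full-N rates.

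The cost is SAP wording, one table category, two lines in Table 18 and a little programming. No new data are needed. The one drawback is that the sensitivity analysis may overstate the early rate, hence its label.
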